1. INTRODUCTION

1.1. Indication

Tofacitinib is being developed for the treatment of adult subjects with active Psoriatic Arthritis (PsA).

1.2. Background and Rationale

Psoriatic arthritis (PsA) is a chronic inflammatory autoimmune disease characterized by joint inflammation and destruction, psoriatic skin lesions, enthesitis, dactylitis, spondylitis, progressive disability and adverse effects on quality of life.^{1,2} Treatment recommendations for the cardinal clinical manifestations of the disease have been developed in recent years by a consensus of rheumatologists and dermatologists.⁴¹ Treatment of subjects with PsA is frequently influenced by the severity of each domain and treatment recommendations vary depending on what disease domain is more severely affected.^{43,44} Some of the agents recommended for the treatment of PsA include non-steroidal anti-inflammatory drugs (NSAIDs), intra-articular glucocorticoid injections, conventional synthetic (cs) DMARDs and TNF inhibitors.^{42,44} The csDMARDs are either prescribed as monotherapy or in combination with other agents.⁴³ Methotrexate (MTX) is a widely used csDMARD for the treatment PsA and commonly one of the first agents administered to patients.^{42,43,44} Despite its popular use, there are only a few randomized placebo controlled trials comparing MTX to placebo in the treatment of PsA and none of them have clearly demonstrated efficacy of this therapy.⁴⁴ One of the few placebo-controlled trials of MTX in psoriatic arthritis failed to find evidence for MTX improving synovitis and showed no advantage of MTX over placebo with respect to rheumatology related global responses.⁴⁵ MTX is frequently used in combination with other therapies also recommended for the treatment of PsA, such as biologics or other csDMARDs.^{42,43,44} Liver toxicity and other secondary effects related to the long term use of MTX continue to be a concern for treating physicians and patients.⁴² Understanding the disease activity of subjects that discontinue one of the agents in their combination treatment will help the medical community determine the usefulness of a step down process of treatment.

The majority of subjects who participated in the tofacitinib PsA development program continue therapy on a stable dose of one background DMARD for the duration of their participation in the long term extension study.

This sub-study is designed to assess the efficacy of tofacitinib 5 mg BID as monotherapy after MTX withdrawal compared to tofacitinib 5 mg BID in combination with concomitant MTX. In addition, the sub-study will assess the safety and tolerability of tofacitinib 5 mg BID as a treatment for PsA in a MTX withdrawal population.

1.2.1. Single Reference Safety Document (SRSD)

Complete information for tofacitinib may be found in the single reference safety document (SRSD, which for this study is the tofacitinib IB. The SRSD for methotrexate is the Summary of Product Characteristics (SPC).

2. STUDY OBJECTIVES AND ENDPOINTS

2.1. Objectives

2.1.1. Primary Objective

- To assess the efficacy of tofacitinib 5 mg BID monotherapy as compared to tofacitinib 5 mg BID with background MTX in subjects who have received prior treatment of tofacitinib in combination with MTX.

2.1.2. Secondary Objective

- To assess the safety and tolerability of tofacitinib 5 mg BID monotherapy as compared to tofacitinib 5 mg BID with background MTX in subjects who had received prior treatment of tofacitinib in combination with MTX.

2.2. Endpoints

2.2.1. Primary Endpoints

- Change from baseline (Δ) in HAQ-DI at 6 months.
- Δ PASDAS at 6 months.

2.2.2. Secondary Endpoints

- Δ HAQ-DI score at all time points except Month 6.
- Δ PASDAS at all time points except Month 6.
- Psoriatic Arthritis Response Criteria (PsARC) response at all time points.
- Δ in Physician's Global Assessment of Psoriasis (PGA-PsO) at all time points.
- $\% \Delta$ in BSA at all time points.
- Δ in Dactylitis severity score at all time points.
- Dactylitis absence at all time points.
- Δ in Enthesitis score (using Leeds Enthesitis Index, [LEI]) at all time points.
- Enthesitis absence (using LEI) at all time points.
- MDA response at all time points.

- Δ in ACR components (tender/painful joint count (68), swollen joint count (66), Physician's Global Assessment of Arthritis, Patient's Global Assessment of Arthritis, Patient's Assessment of Arthritis Pain, CRP) at all time points.
- Physical function/other patient reported outcomes to be assessed at all time points:
 - Δ in Short-Form 36 (version 2, Acute) (8 domains and Physical Component Summary [PCS] score and Mental Component Summary [MCS] score);
 - Δ FACIT-F (Total score, Experience domain and Impact domain scores);
 - Δ EuroQol-5D Health Questionnaire (EQ-5D) (Scores from the five domains and an EQ-Visual Analog Scale (VAS) score on the subject's health state today (EQ-VAS).
- Incidence and severity of adverse events.
- Incidence of clinical abnormalities and change from baseline in clinical laboratory values during treatment.

2.2.3. Other Endpoints

- Δ DAS28-3 (CRP) at all time points.
- MDA component response at all time points.
- Δ in Patient's Global Joint and Skin Assessment (PGJS-VAS) at all time points.
- Incidence of investigator-reported clinically significant changes in physical examination from baseline during treatment.
- Incidence of electrocardiogram (ECG) abnormalities and change from baseline in ECG measurements during treatment.
- Incidence of vital sign (blood pressure and pulse rate) abnormalities and changes from baseline in vital sign measurements during treatment.

3. SUB-STUDY DESIGN

This sub-study within Study A3921092 is a Phase 3, randomized, double-blind, placebo-controlled, parallel group estimation study designed to assess the efficacy, safety and tolerability of tofacitinib 5 mg BID versus tofacitinib 5 mg BID in combination with concomitant MTX in subjects with active PsA. Subjects with active PsA will have previously completed at least 24 months of treatment with tofacitinib in Study A3921092 and will be on a stable dose of tofacitinib 5 mg BID for at least 3 months prior to the first dose of sub-study drug and be on a stable dose of oral MTX at least 4 weeks prior to the first dose of sub-study drug. This sub-study will be referred to as A3921092 Sub-study. For subjects who are

qualified to enter into the sub-study, the Combined A3921092 Sub-study Switch/Baseline visit will occur at a scheduled study visit at or after Month 24 of A3921092. There will be no separate Baseline visit for the sub-study. The visit window will remain as in the LTE in which a month is considered 28 days. Once a subject enters the sub-study, they will complete their participation in the sub-study portion and be unable to re-enter the main study. Subjects may be discontinued from the sub-study at any time during the sub-study in the event of deterioration of response as determined by the investigator.

Eligible subjects from study A3921092, will be randomized into A3921092 sub-study in a 1:1 ratio to tofacitinib 5 mg BID + MTX placebo or tofacitinib 5 mg BID + MTX. MTX will be blinded to the subjects, investigators and the sponsor. The subjects in the tofacitinib 5 mg BID + MTX group will receive blinded MTX capsules (range dose of 7.5-20 mg a week based upon the pre-existing dose) and the subjects in the tofacitinib 5 mg BID group will receive the matching MTX placebo capsules. For the duration of the sub-study tofacitinib dose must remain stable at 5 mg BID. The MTX dose and oral route of administration must remain stable for the 12 month duration of the sub-study. All subjects will receive open-label tofacitinib 5 mg BID throughout the sub-study without dose increase. The total number of subjects randomized will be approximately 180 (Sub-Study [Table 2](#)).

Sub-Study Table 2

Treatment Group	Double blind placebo controlled period	Number of Subjects
B	Tofacitinib 5 mg BID + Placebo	90
C	Tofacitinib 5 mg BID + Methotrexate	90

Treatment duration for subjects participating in this sub-study is approximately 12 months.

At various time points in this trial, safety measurements, including physical examination, clinical laboratory tests, adverse event monitoring, electrocardiograms (ECGs) and vital signs will be performed. All subjects will be monitored for clinical evidence of PsA response to treatment. Health Outcomes Measures (ie, Patient Reported Outcomes assessments for pain, quality of life, physical function, fatigue and health status) will also be performed at various time points in this trial. In addition, subjects will be monitored for serious infections, lymphadenopathy and lymphoproliferative disorder (LPD).

4. SUBJECT SELECTION

This sub-study can fulfill its objectives only if appropriate subjects are enrolled. The following eligibility criteria are designed to select subjects for whom protocol treatment is considered appropriate. All relevant medical and non-medical conditions should be taken into consideration when deciding whether this protocol is suitable for a particular subject.

4.1. Sub-Study Inclusion Criteria

Subject eligibility will be reviewed and documented by an appropriately qualified member of the investigator's study team before subjects are included in the study.

Subjects must meet all of the following inclusion criteria to be eligible for enrollment into the study.

1. Evidence of a personally signed and dated informed consent document indicating that the subject (or a legal representative) has been informed of all pertinent aspects of the study.
2. Subjects who are willing and able to comply with scheduled visits, treatment plan, laboratory tests, and other study procedures.
3. Subjects must have previously completed at least 24 months of treatment with tofacitinib for the treatment of PsA in the long term extension study A3921092.
4. Subjects must be receiving tofacitinib 5 mg BID and be on a stable dose for a minimum of 3 months before the first dose of blinded MTX. Subject receiving tofacitinib 10 mg BID must reduce the tofacitinib dose to 5 mg BID 3 months prior to randomization into the sub-study.
5. Subjects must be receiving oral MTX as their permitted traditional non-biologic background DMARDs, and must be dosed in accordance with the A3921092 requirements.
 - All local standard of care practices for administration of non-biologic background DMARD therapy, including laboratory testing, contraceptive requirements, follow-up care and contraindications, should be performed according to the local standards of care throughout the sub-study.
 - MTX administered orally: Subjects receiving non-oral forms of methotrexate in study A3921092 should switch to an oral route of administration at least 12 weeks before the sub-study entry and remain on it for the duration of the sub-study.
 - Dosing of MTX should be stable (dose range allowed from a minimum dose of 7.5 mg/week and maximum dose of 20 mg/week) 4 weeks prior to entry to the sub-study and remain stable for the duration of it.
 - All subjects should be on an adequate and stable dose of folate supplementation (not less than 5 mg weekly based on folic acid, unless such doses would violate the local label guidelines or standard of care) for at least 4 weeks prior to the first dose of blinded study drug (see [Section 5.6](#)).
6. Subjects who are already taking oral corticosteroids (but not injectable) may participate in the sub-study:
 - Oral corticosteroids: Subjects who are already receiving oral corticosteroids in study A3921092 must remain on a stable dose of ≤ 10 mg/day of prednisone or

equivalent. The dose must be stable for four weeks prior to sub-study entry and remain stable for the duration of the sub-study.

- Subjects who received injectable (eg, intraarticular, intramuscular or intravenous) corticosteroids in study A3921092 should have discontinued their use 12 weeks prior to the of sub-study entry.
7. Subjects who are already taking NSAIDs/COX-2 inhibitors may participate in the sub-study provided that that the dose is stable for one week prior to sub-study entry and remain stable for the duration of it.

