3. STUDY DESIGN

This is a Phase 3, long-term, open-label extension study designed to evaluate the safety, tolerability and efficacy of tofacitinib in subjects with active PsA who have previously participated in randomized PsA clinical studies with tofacitinib. For subjects who complete participation in such a randomized clinical study with tofacitinib, the final visit of the qualifying study can be combined with the screening and baseline visit for this study. Additional assessments and inclusion/exclusion criteria are required for subjects who enroll >14 days after completing treatment in their qualifying study. In this case, a separate screening visit to determine subject eligibility is required followed by a baseline visit.

All eligible subjects from qualifying studies A3921091 and A3921125 will receive open-label tofacitinib 5 mg BID upon entry into A3921092. Subjects from A3921091 will receive first dose of study medication ≥ 1 week after last injection of study medication in that qualifying study. Tofacitinib dose may be increased to 10 mg BID at study visits if, based upon investigator's discretion, subjects receiving tofacitinib 5 mg BID would benefit from a higher dose and are not experiencing any tofacitinib-related adverse events, including abnormalities in laboratory parameters that are judged to be related to tofacitinib. Tofacitinib dose may be decreased (ie, 10 mg BID to 5 mg BID) for safety reasons at any time during the study. Treatment duration for subjects participating in the LTE study is approximately 3 years (36 standardized 4-week months). Subjects participating in the sub-study may have up to an additional 1 year (12 standardized 4-week months) of treatment for a maximum potential total of approximately 4 years (48 standardized 4-week months).

At various time points in this trial, safety measurements, including physical examination, clinical laboratory tests, adverse event monitoring, electrocardiograms (ECGs) and vital signs will be performed. All subjects will be monitored for clinical evidence of response of PsA to treatment. Health Outcome Measures (ie, Patient Reported Outcomes assessment questionnaires for pain, quality of life, physical function, fatigue, work limitations, health care resource utilization and health status) will also be performed at various time points in this trial. In addition, subjects will be monitored for serious infections, lymphadenopathy and lymphoproliferative disorder (LPD).

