5.8. Dosage Reduction and Withholding

All subjects will receive tofacitinib 5 mg BID upon entry into A3921092. Dosage of tofacitinib may be increased to 10 mg BID only at scheduled study visits to provide greater control of the subject's PsA, if the investigator feels the subject would benefit and the subject is not experiencing any tofacitinib-related adverse events, including abnormalities in laboratory parameters that are judged to be related to tofacitinib.

For those subjects whose tofacitinib dose has been increased to 10 mg:

- Dosage of tofacitinib may be reduced back to 5 mg BID for mild to moderate cytopenias, other mild to moderate AEs, or any other safety-related issues, either temporarily or for the duration of the study.
- Definitions of mild to moderate cytopenias are as follows:
 - Mild to moderate neutropenia: 1000-1500 neutrophils/mm³, confirmed;
 - Mild to moderate anemia: a decrease of hemoglobin from 1.0-2.0 g/dL from baseline, inclusive, provided the hemoglobin remains >8.0 g/dL;
 - Mild to moderate thrombocytopenia: 75,000-100,000 platelets/mm³.

For all subjects:

- Dosage of tofacitinib may be temporarily discontinued for up to 28 consecutive days, for more severe cytopenias, for infections which do not meet criteria for serious infections (ie, those requiring parenteral antimicrobial therapy or hospitalization), for surgical procedures or other moderately severe AEs.
- Treatment with tofacitinib will be discontinued and the subject withdrawn from this study for toxicities as defined in [Appendix 4](#).

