Appendix 10. Methotrexate Withdrawal Sub-Study

The purpose of this sub-study is to assess the efficacy, safety and tolerability of tofacitinib 5 mg BID administered as monotherapy after methotrexate (MTX) withdrawal compared to tofacitinib 5 mg BID continued in combination with MTX in subjects with active PsA. Subjects who have completed at least 24 months of participation in the long term extension study A3921092 and are currently receiving methotrexate may be included. Not all countries participating in the LTE will be included in this sub-study.

Subjects will be randomized to the 2 treatment arms in a 1:1 ratio, one in which they will receive open label tofacitinib 5 mg tablets BID and blinded methotrexate capsules (oral dose range from 7.5 mg to 20 mg per week) and the second in which they will receive open label tofacitinib 5 mg tablets BID and blinded MTX placebo capsules. The sub-study will be approximately 12 (standardized 4-week) months in duration and visits will occur at Baseline, Months 1, 3, 6, 9 and 12. The sub-study baseline will occur at the same time as a scheduled study visit at or after Month 24 of A3921092. This visit will be referred to as Sub-study Switch visit or Baseline visit (Sub-study Switch/Baseline visit).

Throughout this Appendix, [Sections 4.5, 7, 8, 9.5 to 15.2](#) will be referenced to the main LTE protocol to avoid duplication.

SUB-STUDY TABLE 1. SCHEDULE OF ACTIVITIES

The Schedule of Activities table provides an overview of the sub-study visits and procedures. Refer to Sub-study Procedures (Section 6) and Assessments (Section 7) for detailed information on each procedure and assessment required for compliance with the protocol.

The investigator may schedule visits (unplanned visits) in addition to those listed on the schedule of activities, in order to conduct evaluations or assessments required to protect the wellbeing of the subject.

Protocol Activity	Combined A3921092 Sub-study Switch/Baseline ¹	Sub-study Month 1 (±7 days)	Sub-study Month 3 (±7 days)	Sub-study Month 6 (±7 days)	Sub-study Month 9 (±7 days)	Sub-study Month 12 Or Early Termination (±7 days)	Follow-up Visit (28 days ±7) ²
Informed Consent	X						
Register for subject identification number and Randomization	X						
Complete Physical Exam ⁴	X					X	
Targeted Physical Exam ⁴		X	X	X	X		
Vital signs, temperature		X	X	X	X	X	
Waist and hips circumference			X	X	X	X	
Cardiovascular Risk Assessment ³	X					X	
12-Lead ECG ⁵	X					X	

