4.2. Sub-Study Exclusion Criteria

Subjects presenting with any of the following characteristics/conditions will not be included in the study:

1. Subjects who are receiving other concomitant non-biologic csDMARDs, eg, leflunomide, sulfasalazine.
2. Subjects receiving MTX by a route other than oral.
3. Subjects receiving MTX at a dose lower than 7.5 mg per week or >20 mg per week.
4. Subjects who are investigational site staff members directly involved in the conduct of the trial and their family members, site staff members otherwise supervised by the investigator, or subjects who are Pfizer employees directly involved in the conduct of the trial.
5. Subjects that have become pregnant during study A3921092 and breastfeeding females and females of child-bearing potential who are unwilling or unable to use a highly effective method(s) of contraception as outlined in this protocol for the duration of the study and for at least one ovulatory cycle after last dose of investigational product or females planning pregnancy.
6. Women of childbearing potential must test negative for pregnancy prior to enrollment in this study. (Further description of the requirements and a list of contraceptives considered highly effective and acceptable for use in this study will be found in [Section 4.4.6](#)).
7. Current or recent history of uncontrolled renal, hepatic, hematological, gastrointestinal, metabolic (including hypercholesterolemia), endocrine, pulmonary, cardiovascular, or neurologic disease.
8. Subjects who have been diagnosed with any autoimmune rheumatic disease other than PsA (including systemic lupus erythematosus, mixed connective tissue disease, scleroderma, polymyositis) or diagnosis of fibromyalgia, without approval by Sponsor. Also excluded are subjects with prior history of, or current, rheumatic

- inflammatory disease other than PsA (eg, gout, reactive arthritis, chronic Lyme disease) without approval by Sponsor.
9. A subject who has been diagnosed with immunodeficiency disorder during study A3921092.
 10. Functional Class IV status as defined by the American College of Rheumatology classification of functional status for RA, ie, limited in ability to perform usual self-care, vocational and avocational activities.¹⁵
 11. History of an infected joint prosthesis at any time, with the prosthesis still in situ.

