6. SUB-STUDY PROCEDURES

Subjects from the long term extension study who elect to participate in the sub-study should complete a combined A3921092 Sub-study Switch/Baseline visit on the same day of the scheduled A3921092 study visit at or after Month 24.

The study investigator or a sub-investigator will discuss with each subject the nature of the study, its requirements, and its restrictions. Written informed consent must be obtained prior to performance of any protocol-specific procedures.

Subjects who are on prohibited medications, and are deriving a beneficial response from them, should not be entered into this sub-study. Subjects may be discontinued from the sub-study at any time during the sub-study in the event of deterioration of response as determined by the investigator.

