6.1. Combined A3921092 & Sub-Study Switch/Baseline Visit

The Combined A3921092 Sub-study Switch/Baseline visit occurs at Month 24, Month 27, Month 30, Month 33, or Month 36 of A3921092. Since not all of the study procedures and assessments needed for the Baseline of the sub-study are collected at these visits of A3921092, any assessment or activity that was not completed as part of the A3921092 visit needs to be completed at this combined visit. At the Switch/Baseline visit of the sub-study, all investigational product from the main A3921092 LTE study will be collected for accountability under the main protocol. New tofacitinib supplies will be dispensed under the sub-study. Details of the required activities are listed below.

Subjects are required to fast for at least 9 hours prior to the visit. Blood collection may be taken up to 48 hours prior to or following this visit as necessary to ensure samples are collected in a fasted state.

All Patient Reported Outcomes should be completed prior to any other study procedures.

6.1.1. Combined A3921092 & Sub-Study Switch/Baseline Visit at Month 24 or Month 36

For subjects with the Combined A3921092 Sub-study Switch/Baseline visit conducted at the scheduled A3921092 study visit of Month 24 (M24) or Month 36 (M36), subjects must complete activities as indicated from M24 or M36 visit of A3921092 in addition to the following procedures:

- Informed consent obtained.
- Collect tofacitinib LTE investigational product supplies and complete accountability for the last visit of the main LTE study.
- Register for subject identification number.
- Randomization completed.
- Dispense study medication/schedule next visit.
- Observe subject taking the study drugs (tofacitinib and MTX or placebo) and record the dosing in the dosing log CRF.

6.1.2. Combined A3921092 & Sub-Study Switch/Baseline Visit at Month 27 or Month 33

For subjects with the Combined A3921092 Sub-study Switch/Baseline visit conducted at the scheduled A3921092 study visit of Month 27 or Month 33, the subjects must complete activities as indicated from M27 or M33 visit of A3921092 in addition to the following procedures.

- Informed consent obtained.
- Collect tofacitinib LTE investigational product supplies and complete accountability for the last visit of the main LTE study.
- Register for subject identification number.
- Randomization completed.
- SF-36 Version 2 (Acute).
- FACIT-F.
- EQ-5D.

The following additional procedures will also be performed:

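### Subjects who step down from 10 to 5 mg BID only to enter the methotrexate-withdrawal sub-study must do so at least 84 days before the only scheduled sub-study consent

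*Protocol*

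**What the plan says.** **The qualifying change.** Criterion 4 in Protocol Appendix 10, Section 4.1 requires a stable 5 mg BID dose for a minimum of 3 months before blinded methotrexate (MTX) starts, and adds: "Subject receiving tofacitinib 10 mg BID must reduce the tofacitinib dose to 5 mg BID 3 months prior to randomization into the sub-study". Criterion 5 has a softer counterpart for MTX route: "Subjects receiving non-oral forms of methotrexate in study A3921092 should switch to an oral route of administration at least 12 weeks before the sub-study entry". Exclusion 2 in Section 4.2 then rules out "Subjects receiving MTX by a route other than oral".

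**Where consent is scheduled.** In Sub-Study Table 1 the consent row is marked only in the Switch/Baseline column. So is the row "Register for subject identification number and Randomization". Sections 6.1.1 to 6.1.3 each list "Informed consent obtained" at that visit, together with randomization. Appendix 10, Section 3 says there is no separate baseline visit. The main-study list for the Month 21 visit (Section 6.2.2) has no consent step.

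**The consent rules.** Appendix 10, Section 6 says: "Written informed consent must be obtained prior to performance of any protocol-specific procedures". Main protocol Section 12.3, which Appendix 10 adopts by reference, requires written consent before any activity specific to the study. Appendix 10, Section 4.3 makes the sub-study consent a document of its own.

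**Grounds for reducing the dose in the LTE.** Section 3: "Tofacitinib dose may be decreased (ie, 10 mg BID to 5 mg BID) for safety reasons at any time during the study". Section 5.8: the dose "may be reduced back to 5 mg BID for mild to moderate cytopenias, other mild to moderate AEs, or any other safety-related issues". Appendix 4.2 allows reductions for adverse events and confirmed laboratory abnormalities. Section 5 confines dose changes to scheduled visits, except for reductions needed for safety.

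**The concern.** A subject is on 10 mg BID because the investigator judged symptoms inadequately controlled on 5 mg BID (Section 5, Appendix 4.2). Going back to 5 mg BID with no safety reason, in order to enter an optional study, exposes that subject to possible loss of control. The sub-study then holds the dose at 5 mg BID with no increase, may replace MTX with placebo, and does not allow return to the main LTE (Appendix 10, Section 3). Those facts bear on the decision to reduce, yet the documented consent that conveys them is scheduled only after the reduction has been in place for about three months.

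The main protocol does offer some protection in the meantime. Background therapy can be adjusted (Section 5.6.1), unplanned visits are possible (Schedule of Activities), and rescue medication is allowed for up to 10 consecutive days (Section 5.7). A return to 10 mg BID has to wait for a scheduled visit (Appendix 4.2).

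**Working it through.** **Inputs**
- Lead time for the dose reduction: 3 months (Appendix 10, Section 4.1, criterion 4).
- Length of a study month: 28 days (Appendix 10, Section 3).
- Lead time for the MTX route switch: 12 weeks (criterion 5).
- Target days (SAP Appendix 1): Month 21 = 589, Month 24 = 673, Month 27 = 757, Month 30 = 841, Month 33 = 925, Month 36 = 1009.
- Visit window: ±10 days at each of these visits (Protocol Sections 6.2.2 to 6.2.4).
- Scheduled consent: same visit as randomization, so 0 days before it.

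**Step 1. The required lead time.** 3 × 28 = 84 days. The MTX route switch gives the same figure: 12 × 7 = 84 days.

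**Step 2. How this fits the visit grid.** 673 − 589 = 757 − 673 = 841 − 757 = 925 − 841 = 1009 − 925 = 84 days. The lead time is exactly one nominal visit interval. A non-safety dose change is tied to a scheduled visit, so the latest reduction visits for entry at Months 24, 27, 30, 33 and 36 are Months 21, 24, 27, 30 and 33.

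**Step 3. Time on the reduced dose before scheduled consent, entry at the next visit.** With both visits free to move by 10 days, the interval runs from 84 − 20 = 64 to 84 + 20 = 104 days. Only intervals of at least 84 days satisfy criterion 4, so the range for entrants is 84 to 104 days.

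**Step 4. First interval too short.** A subject whose first interval is 64 to 83 days must wait for the following visit. Two nominal intervals are 2 × 84 = 168 days.
- Shortest: reduction visit 10 days late, entry visit 10 days early, 168 − 20 = 148 days.
- Longest: for the first interval to be 83 days or less, the reduction visit must lie at least one day later, relative to its target, than the next visit. That next visit can be at most 10 days early, so the reduction visit can be at most 9 days early. With entry 10 days late: 168 + 9 + 10 = 187 days.

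The range is 148 to 187 days. It does not apply to a subject who reduces at Month 33, because Month 36 is the last entry visit.

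**Step 5. Is the reduction study-specific?** Section 3, Section 5.8 and Appendix 4.2 all tie a step from 10 to 5 mg BID to safety or tolerability. None names a reduction made to qualify for the sub-study. On those sections, a reduction with no safety reason exists only because of criterion 4, and the consent-first rules would cover it. Section 5 is the exception: it regulates when a dose may change and can be read as allowing a non-safety change at any scheduled visit.

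**The case against.** The best answer to this point has four parts.

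1. *No visit list schedules the reduction.* A reader might infer that the protocol directs sites to act without consent, or that any site following the visit lists breaks the consent rules. The documents do not support that. The lists cover the sub-study's own procedures and put consent at the same visit. Nothing forbids earlier consent, and the general rules would require it for a study-specific act. A breach arises only if a site reduces the dose solely to qualify and takes consent only at Switch/Baseline. This stands, and it limits the point to a scheduling gap.

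2. *The reduction may be an ordinary LTE dose change.* Section 5 can be read that way, the list of other adjustments in Appendix 4.2 is not worded as exhaustive, and 5 mg BID is the dose on which every LTE subject starts. This stands in part. Section 5 says when a dose may change but gives no non-safety reason for lowering it, and the sections that do give reasons name safety.

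3. *The LTE consent form might already cover a qualifying change.* It is not among the reviewed documents, so this can be neither shown nor excluded, and its absence from the file is not a fault in the plan.

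4. *Few subjects may be affected.* The Protocol Summary describes candidates as already on 5 mg BID with oral MTX, and such subjects are untouched. No count of subjects on 10 mg BID who would step down is given. This stands.

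The MTX route case is weaker. Criterion 5 uses advisory wording, although exclusion 2 still makes oral MTX an entry condition. Before enrollment MTX is the subject's own commercial supply, managed to local standards.

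**Conclusion.** The point holds for a defined subset: subjects on 10 mg BID who step down only to meet criterion 4. For them the protocol requires the change at least 84 days before randomization but schedules sub-study consent on the day of randomization. If consent is taken only where it is scheduled, it follows 84 to 104 days on the reduced dose, or 148 to 187 days where the first interval falls short and a later entry visit exists.

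This rests on three assumptions: the 3 months are counted in 28-day study months; the reduction is made at a scheduled LTE visit within its window; and a reduction made only to qualify is study-specific. The third is the better-supported reading but is not beyond dispute.

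A reader might also infer that the sub-study comparison is compromised. It is not: consent timing changes no endpoint, randomization step or precision figure. What is at stake is subject protection and agreement between the schedule and the consent rules. This is a cheap improvement worth making, not a flaw in the statistical design.

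**What to change.** Add to Appendix 10, Section 6.1, with a matching entry in Sub-Study Table 1:

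> Subjects who will reduce tofacitinib from 10 to 5 mg BID, or change MTX route, solely to qualify for the sub-study must sign the sub-study consent at or before the scheduled LTE visit where the change is made, and before the change. Eligibility, registration and randomization remain at Switch/Baseline. AE/SAE reporting stays under the LTE subject number until randomization.

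The last sentence is needed because SAE reporting starts at consent (Section 8.2), while the sub-study subject number is assigned only at enrollment (Appendix 10, Section 4.3). Without it, a subject who consents early could be reported under both parts of the study for about 84 days.

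The cost is one earlier consent step at an existing visit, and some subjects will consent and not be randomized. No visits or subjects are added.
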